6. STUDY PROCEDURES

6.1. Study Schedule

All required study procedures are listed by visit in Appendix A, Appendix B and Appendix C.

6.1.1. Screening

Written informed consent for the study will be obtained prior to the performance of any study-related procedures including screening procedures. A 6-week period is provided for completing screening assessments and determining patient eligibility for the study. Safety labs may be re-tested up to 2 additional times for determination of patient eligibility.

During the Screening Period, patients will undergo a medical history (including cardiovascular disease risk factors) and physical examination including vital signs, orthostatic hypotension assessment, 12-lead ECG, and have blood and urine samples taken for clinical laboratory testing. Patients will be screened for HIV, HepB, and HCV.

During the Screening Period the study site will also educate patients regarding adequate hydration and low sodium diet.

A 24-hour blood pressure (BP) monitoring will be performed during the Screening Period.

The study site will record basic personal details, including name, contact details, gender, height, weight, date of birth, age, ethnicity, and racial origin (to be used only for clinical purposes), as well as information on medical history, and clinical data collected about the patient's participation in the study.

6.1.1.1. 24-Hour Ambulatory Blood Pressure Monitoring

A 24-hour ABPM, conducted with a Sponsor provided machine, will be assessed during the Screening Period and at one additional time point for patients who have received 8 or more doses as detailed in the Appendix A Schedule of Procedures.

The assessment should take place after the Screening Visit 1 blood pressure, pulse pressure, and labs have been resulted, the results are deemed not to be exclusionary, and blood pressure is confirmed not to be exclusionary at Screening Visit 2. Ensure sufficient time during the Screening Period to allow for a repeat (if the first 24-hr monitoring is not successful) prior to the Study Day 1 visit.

For patients who have been administered 8 or more doses of Study Drug, 24-hr ABPM should ideally be initiated in-clinic after all other study procedures have been completed either on Study Day 78 or Day 85 (completed 12 doses) or Treatment Early Termination/Study Day 85 (completed 8-11 doses). If a repeat is necessary, the 24-hr ABPM should be initiated no later than the Study Day 92 visit. Ensure the 24-hr ABPM is not done concurrently with other study procedures.

Please refer to the Study Manual for additional details.

6.1.1.2. Seated Automated Office Blood Pressure Measuring Instructions at Each Visit

The seated automated office blood pressure monitoring is to be conducted with Sponsor provided blood pressure machines throughout the study.

Patient Instructions

- Patient should have abstained from smoking, exercise and caffeine use at least 30 minutes prior to BP measurements
- Patient should be wearing a loose, short-sleeved top. If patient is wearing a long-sleeved or tight garment around the arm, provide a gown or remove the arm from the sleeve
- Patient should be comfortably seated (e.g., with his/her back against the chair, feet flat on the floor)
- Patient's arm should be bent at the elbow and supported by a table

Observer Instructions

- Confirm with that the patient has abstained from smoking, exercise and caffeine use at least 30 minutes prior to measurement
- Place the seated automated office blood pressure cuff on the patient's upper arm at the level of the heart and centered at the midpoint of the humerus
- Leave patient alone for 5 minutes in a quiet setting
- After 5 minutes, return and take 3 readings, with approximately 2-3 minutes between readings
- Document the average of the 3 readings

Screening Visit 1 BP Results

At the Screening Visit 1, measure the BP per instructions above with both the right and left arm. The arm with the highest SBP (that meets inclusion/exclusion criteria) and meets the Pulse Pressure criteria should be used at each subsequent visit.

6.1.1.3. Orthostatic Blood Pressure Assessment

An orthostatic BP assessment will be done at Screening Visit 1. BP and pulse rate will be assessed 2 times (Table 2). The patient will lie down (supine) for at least 5 minutes, then BP and pulse rate will be measured. The patient will then change to a standing position and the BP and pulse rate measurements will be repeated after standing greater than 1 minute, but less than or equal to 3 minutes. Up to 1 additional test may be done once the patient is adequately hydrated if orthostasis is thought to be attributed to volume depletion.

Borderline orthostatic hypotension will be defined as a confirmed (sequence must be repeated to confirm) decrease in SBP \geq 15 mmHg from BP at supine position.

Table 2: Orthostatic Hypotension Assessment

Position	Time in Position	Vital Signs Assessed
Supine	5 minutes	BP and pulse rate after 5 minutes
Standing	> 1 to ≤ 3 minutes	BP and pulse rate assessed within > 1 to ≤ 3 minutes of standing

6.1.2. Treatment Period

Eligible patients will be administered Study Drug (ISIS 757456 or placebo) on a weekly basis (12 weeks) for a total of 12 doses. Measurement and review of the in-clinic BP should be performed on the same day prior to administering the Study Drug. Of the 12 required study visits during the Treatment Period, 11 selected study visits have the option for Home Healthcare (a Sponsor approved vendor). Home Healthcare assessments and procedures may be conducted by a Home Healthcare professional at specified visits per the Schedule of Procedures (Appendix A) and as arranged by site staff. If 3 consecutive Home Healthcare visits have been conducted, the Sponsor must be consulted prior to the scheduling of a 4th in-home visit. The Home Healthcare visit must be conducted by a Home Healthcare professional that is appropriately trained prior to a Home Healthcare visit. If a visit cannot be performed in the clinic or by a Home Healthcare professional, patient contact (e.g., video call, text, email, etc.) is required by site personnel to assess any AEs, changes in concomitant medications, adequate hydration and low sodium diet counseling.

Safety and clinical laboratory evaluations as well as blood sampling for PK analysis will be performed periodically throughout the Treatment Period (Appendix A, Appendix B, and Appendix C). Any AEs and concomitant medications will be recorded. At each visit, qualified site staff will review vital signs and laboratory results prior to each dosing to ensure compliance with monitoring and stopping rules outlined in Section 8.

The patient is expected to maintain adequate hydration and a low sodium diet throughout the study. The study site will counsel and ask the patient at each in-clinic visit if (s)he is maintaining adequate hydration and a low sodium diet.

Patients who discontinue the Treatment Period early will continue in the study following the post-treatment evaluations (Section 6.1.3).

All safety data including AEs, BP, and concomitant medications will be reviewed by the Sponsor's Medical Monitor or designee on an ongoing basis throughout the trial

6.1.3. Post-Treatment Period

After the last dose (Study Day 78) or last dose for early termination patients, patients will return to the clinic once weekly for the first 2 weeks (Study Days 85, 92) and then on Study Days 106, 120, 148, and 169 for safety assessments.

The study site will continue to counsel and ask the patient at each visit if (s)he is maintaining adequate hydration and a low sodium diet in the Post-Treatment Period.

For patients who have been administered 8 or more doses of Study Drug, the second 24-hr ABPM will be conducted. This 24-hr APBM should ideally be initiated in-clinic after all other study procedures have been completed either on Study Day 78 or Treatment Early Termination/Study Day 85. If a repeat is necessary, the 24-hr ABPM should be initiated no later than the Study Day 92 visit. Ensure the 24-hr ABPM is not done concurrently with other study procedures.

All safety data including AEs, in-clinic BP, and concomitant medications will be reviewed by the Sponsor's Medical Monitor or designee on an ongoing basis throughout the trial.

Of the 6 required study visits during the Post-Treatment Period, 4 selected study visits have the option to be performed outside the clinic by a Sponsor selected Home Health Care professional. Home Healthcare assessments and procedures may be conducted by a Home Healthcare professional at specified visits per the Schedule of Procedures (Appendix A) and as arranged by site staff. If 3 consecutive Home Healthcare visits have been conducted, the Sponsor must be consulted prior to the scheduling of a 4th in-home visit. If a visit cannot be performed in the clinic or by Home Health Care, patient contact (e.g., video call, text, email, etc.) is required by site personnel to assess any AEs, changes in concomitant medications, adequate hydration and low sodium diet counseling.

6.2. Laboratory Assessments

Laboratory analyte samples will be collected throughout the study. A list of these analytes is contained in Appendix B.

If the platelet value, eGFR, UPCR, potassium, or liver enzyme tests are uninterpretable (e.g., due to clumping, hemolysis, or quantity not sufficient) or missing a repeat blood specimen should be re-drawn as soon as possible (ideally within 7 days, either in clinic, by Home Healthcare or local laboratory). Any uninterpretable platelet count, eGFR, UPCR, liver enzyme, or potassium result must be rechecked and determined not to have met a stopping rule before dosing can continue. If Day 1 results are uninterpretable, Day 8 dosing may proceed, however, an interpretable result is required (and must be reviewed) before study drug dosing on Day 15. If there is suspicion of EDTA mediated platelet clumping, a repeat platelet count should be collected in a sodium citrate tube as soon as possible. Treatment should be held if there is no evaluable platelet count within 18 days prior to the scheduled dose (Section 8.5.2).

6.3. Patient Reported Outcomes

The assessments listed in the sections below should be, ideally, performed prior to any interventional study procedures, such as blood draws and vital signs. Appropriate instructions will be provided to the patient by site staff.

6.3.1. Patient Global Impression Items

The Patient Global Impression- Change (PGI-C) is a questionnaire which asks the patient to rate the perceived level of improvement (or worsening) in the patient's hypertension since the start of study treatment, using categorical response options. The Patient Global Severity- Change (PGI-S) is a questionnaire which asks the patient to rate his or her current hypertension disease severity, using categorical response options. The assessments may take approximately 3 to 5 minutes each to complete.

6.3.2. EuroQol-5 Dimension 5 Level (EQ-5D-5L)

The EQ-5D-5L is a two-part, self-reported instrument that assesses the patient's health state. The patient must self-rate their level of severity for five dimensions that include mobility, self-care, usual activities, pain/discomfort, and anxiety/depression. In a second part of the assessment, the patient must report their perceived health on a visual analog scale ranging from 0 to 100. The questionnaire may take approximately 3 to 5 minutes to complete.

6.3.3. 12-Item Short Form Survey (SF-12)

Patients will be asked to complete the SF-12, which is a set of generic, coherent, and easily administered quality of life measures. The SF-12 consists of 12 questions that measure 8 health domains: general health, physical functioning, role physical, bodily pain, vitality, social functioning, role emotional, and mental health. The assessment should take approximately 3 to 5 minutes to complete.

6.3.4. Power Over Pressure- Hypertension Specific Questionnaire (POP-HSQ)

The POP-HSQ is a disease specific patient reported questionnaire which assesses the patient's severity and frequency of nonspecific symptoms associated with hypertension and mental health as impacted by hypertension. The assessment may take approximately 15 minutes to complete.

6.4. Restriction on the Lifestyle of Patients

6.4.1. Contraception Requirements

All male and female patients must refrain from sperm/egg donation from the time of signing the informed consent until at least 20 weeks after the patient's last dose of study treatment.

Males must be abstinent[†], or if engaged in sexual relations with a woman of childbearing potential, highly effective contraception must be used from the time of signing the informed consent until at least 20 weeks after the patient's last dose of study treatment.

For the purposes of this study, WOCBP are defined as any female who has experienced menarche, and who does not meet one of the following conditions:

- Postmenopausal: 12 months of spontaneous amenorrhea in females > 55 years of age
 or, in females ≤ 55 years, 12 months of spontaneous amenorrhea without an
 alternative medical cause and FSH levels in the postmenopausal range for the
 laboratory involved
- 6 weeks after surgical bilateral oophorectomy with or without hysterectomy
- Post-hysterectomy

[figure not shown]
For the purposes of the study, highly effective contraception is defined as follows:

- For males: surgical sterilization (vasectomy with negative semen analysis at follow-up), a surgically sterile non-pregnant female partner, or the non-pregnant female partner of WOCBP uses a highly effective contraceptive method (defined below)
- For female partners of male subjects: surgical sterilization (e.g., bilateral tubal occlusion, hysterectomy, bilateral salpingectomy, bilateral oophorectomy), hormonal contraception associated with inhibition of ovulation (combined estrogen and progestogen containing, or progestogen-only), intrauterine contraception device or intrauterine hormone-releasing system (IUS).

Male patients with partners that are pregnant must use condoms as barrier method to ensure that the fetus is not exposed to the Study Drug.

†Note: Abstinence (i.e., refraining from heterosexual intercourse throughout the duration of study participation) is only acceptable as true abstinence, i.e., when this is in line with the preferred and usual lifestyle of the patient. Periodic abstinence (e.g., calendar, ovulation, symptothermal, post-ovulation methods), declaration of abstinence for the duration of a trial and withdrawal are not acceptable methods of contraception.

7. STUDY DRUG

7.2. Packaging and Labeling

The Sponsor will provide the Investigator with packaged Study Drug (ISIS 757456 or placebo) labeled in accordance with specific country regulatory requirements.

7.3. Study Drug Accountability

The study staff is required to document the receipt, dispensing, and return/destruction of Study Drug (ISIS 757456 or placebo) supplies provided by the Sponsor according to Sponsor instruction and in accordance with institutional policy.

8. TREATMENT OF PATIENTS

8.1. Study Drug Administration

Please refer to the Study Drug Manual provided by the Sponsor for more detailed instructions for Study Drug (ISIS 757456 or placebo) preparation and administration.

Table 4: Study Drug Dosing Information

Cohort	Total Dose
Cohort A	80 mg ISIS 757456 or placebo SC
Cohort B	120 mg ISIS 757456 or placebo SC

^{*} The administration of Study Drug for doses of 120 mg may be delivered as a single injection or 2 non-contiguous injections.

8.2. Other Protocol-Required Drugs

Per eligibility criteria, patients must be on a stable regimen of 3 antihypertensives for at least 1 month prior to screening evaluations and will be required to continue the stable regimen throughout the duration of the study (Refer to Inclusion Criteria Section 5.1).

8.3. Other Protocol-Required Treatment Procedures

There are no other protocol-required treatment procedures.

8.4. Treatment Precautions

There are no treatment precautions required.

8.5. Safety Monitoring Rules

Please refer also to the 'Guidance for Investigator' section of the Investigator's Brochure.

For the purposes of safety monitoring Baseline is defined as:

• The last non-missing measurement prior to the first dose

In addition to the standard monitoring of clinical safety parameters, the following guidelines are provided for the monitoring of selected parameters chosen based on preclinical and clinical observations.

Confirmation Guidance: At any time during the study (Treatment or Post-Treatment Periods), the initial clinical laboratory results meeting the safety monitoring criteria presented below **must be confirmed** by performing measurements (ideally in the same laboratory that performed the initial measurement) on new specimens. All new specimen collections should take place as soon as possible (ideally within 3 days of the initial collection). For stopping rules, if the initial laboratory result is observed during the Treatment Period, the results from the retest **must be available** prior to administering the next dose of Study Drug (ISIS 757456 or placebo).

Re-dosing Guidance: Patients with initial laboratory test values that reach a stopping rule must not be re-dosed until the re-test results are available. In general, patients who do not meet the stopping rules based upon retest may continue dosing. However, the Investigator and the Sponsor Medical Monitor (or appropriately qualified designee) should confer as to whether additional close monitoring of the patient is appropriate. If any of the stopping criteria described below (refer to Sections 8.6.1 to 8.6.6) are met, the patient will be permanently discontinued from further treatment with Study Drug (ISIS 757456 or placebo), evaluated fully as outlined below and in consultation with the Sponsor Medical Monitor or appropriately qualified designee, and will be followed up in accordance with Section 8.8 of the protocol.

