Section 8.6 Stopping Rules	For the purposes of the stopping rules, Baseline is defined as: • Temporary stopping rules for renal function tests • Baseline is defined as the average of the predose test closest to Day 1 and Day 1 last non missing measurement prior to the first dose • Stopping rules for platelets – Baseline is defined as the last non missing measurement prior to the first dose	The definition of baseline for renal stopping rules was modified in order to provide a more accurate pre-dose clinical status while taking physiological variability into consideration. This will better indicate if additional monitoring or the stopping of Study Drug is necessary.
Section 8.6.2 Stopping Rules for Renal Function Test Results	1.Confirmed 30% decline in eGFR from Baseline eGFR values [eGFR should be calculated using the CKD-EPI creatinine equation (Levey et al. 2009)] 2. Confirmed proteinuria (UPCR ≥ 0.7 mg/mg): Absolute UPCR value ≥ 1000 mg/g The follow up schedule for any events meeting either of these stopping criteria will be determined by the Investigator in consultation with the Sponsor Medical Monitor or designee. The possible dosing re-initiation or follow-up schedule for any events meeting either of these criteria will be determined by the Investigator in consultation with the Sponsor Medical Monitor or designee. At the discretion of the Investigator, a decision to hold or permanently stop study drug may be made based on lesser changes in these parameters observed in isolation or in association with other renal-related abnormalities.	The renal function monitoring and stopping rules were updated to align with the modified eligibility criteria based on the collective renal safety and laboratory data currently available across ISIS 757456 clinical studies. The updated language also clarifies the guidelines for Study Drug reinstitution.

Protocol Section	Description of Change	Rationale
Section 8.10.1 Concomitant Therapy	The following are disallowed concomitant therapies: Other medications for the treatment of HTN (e.g., minoxidil, diazoxide, renin inhibitors) Medications that may cause hyperkalemia unless on a stable dose at least 1 month prior to the Screening visit (e.g., eyclosporine or tacrolimus, pentamidine, trimethoprim sulfamethoxazole, all heparins)	The disallowed concomitant therapies were updated to reflect the updated exclusion criterion.

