8.6. Stopping Rules

For the purposes of the stopping rules, Baseline is defined as:

- Temporary stopping rules for renal function tests Baseline is defined as the average of the pre-dose test closest to Day 1 and Day 1
- Stopping rules for platelets Baseline is defined as the last non-missing measurement prior to the first dose

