8.6.2. Stopping Rules for Renal Function Test Results

- 1. Confirmed 30% decline in eGFR from Baseline eGFR values [eGFR should be calculated using the CKD-EPI creatinine equation (Levey et al. 2009)]
- 2. Confirmed proteinuria: Absolute UPCR value ≥ 1000 mg/g

The possible dosing re-initiation or follow-up schedule for any events meeting either of these criteria will be determined by the Investigator **in consultation with** the Sponsor Medical Monitor or designee.

At the discretion of the Investigator, a decision to hold or permanently stop study drug may be made based on lesser changes in these parameters observed in isolation or in association with other renal-related abnormalities.

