8.6.3. Stopping Rule for Platelet Count Results

See Table 5 for an overview of monitoring and stopping rules for platelet counts.

- In the event of a confirmed platelet count less than 50,000/mm³, dosing of a patient with Study Drug (ISIS 757456 or placebo) will be stopped permanently
 - The platelet count should be tested at least twice weekly until 3 successive values above 75,000/mm³
 - Then tested weekly until 3 values above 100,000/mm³
 - Subsequent monitoring should follow the Schedule of Procedures (Appendix A)

- In the event of any platelet count less than 25,000/mm³, dosing of the patient with Study Drug will be stopped permanently
 - Platelet count should be monitored daily until 3 successive values above 25,000/mm³
 - Then monitor at least twice weekly until 3 successive values above 75,000/mm³
 - Then monitor weekly until 3 successive values above 100,000/mm³
 - Then monitor per the Schedule of Procedures (Appendix A)
 - Administration of corticosteroids is recommended for patients whose platelet count is less than 25,000/mm³, with referral to a hematologist.

In the event of a platelet count $< 75,000 / \text{mm}^3$ and $\ge 50,000 / \text{mm}^3$, and in the absence of MB or CRNMB (defined below), dosing with Study Drug should be suspended temporarily until the platelet count has recovered to $> 100,000 / \text{mm}^3$. The suitability of the patient for continued dosing will be determined by the Investigator in consultation with the Study Medical Monitor and will be based on factors such as the original rate of decline in the patient's platelet count, whether any bleeding events were experienced, and the speed of recovery of platelet count after interruption of dosing. If dosing is reinitiated, platelet count must be measured twice weekly (consider more frequent monitoring if risk factors for bleeding are present) until 3 successive values above $75,000 / \text{mm}^3$ then weekly until the end of study. Treatment should be held if there is no evaluable platelet count within 18 days prior to the scheduled dose. Any uninterpretable platelet count result must be rechecked and determined not to have met a stopping rule before dosing can continue.

Labs to Be Performed in the Event of a Platelet Count Less than 50,000/mm³

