8.6.6. Stopping Rule for Blood Pressure

- 1. If the patient remains symptomatic (i.e., dizziness, light-headedness, clammy skin, fatigue, blurry vision) and/or in the event of the average of 2 additional BP measurements ≤ 90 mmHg (systolic) after instituting oral or IV hydration, Study Drug should be permanently discontinued, and the patient should be referred to urgent care or the emergency room.
 - Any other antihypertensives or other medications that could affect BP should be stopped, if feasible. The use of IV angiotensin II or vasopressors should be considered in patients that remain symptomatic and are hemodynamically unstable. The patient will continue to be followed per protocol in the study. Follow-up for patients that screen fail due to BP inclusion criteria (see Section 5.1) will not be necessary.
- 2. Should a patient experience a BP measurement > 180 mmHg (systolic) or > 115 mmHg (diastolic) 2 additional measurements must be done within a 30-minute period and the average must be calculated. If the average of the 2 additional measurements is > 180 mmHg (systolic) or > 115 mmHg (diastolic), they will then be withdrawn from further blinded, randomized treatment. Study Drug is to be permanently discontinued unless the hypertensive event is transient and dependent on reversible initiating factors (e.g., stressful event). The suitability of the patient for continued dosing will be determined by the Investigator in consultation with the Sponsor Medical Monitor after the patient's BP has normalized. Additional antihypertensive medication(s) may be added per Investigator and Sponsor Medical Monitor judgement if the patient has discontinued Study Drug. If the patient has not discontinued Study Drug, changes to the stable regimen of antihypertensives may result in withdrawal of the patient from the Treatment Period. The patient will continue to be followed per protocol in the study. Follow-up for patients that screen fail due to BP inclusion criteria (see Section 5.1) will not be necessary.

Table 7: Blood Pressure Stopping and Monitoring Rules

Confirmed Blood Pressure	Dosing	Additional Actions
SBP ≤ 90 mmHg* and/or patient is symptomatic (e.g., decreased oral	• Pause	Institute oral and/or IV hydration. If hypotension or symptoms of hypotension persist proceed to stopping rules below

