8.8. Discontinuation of Study Drug

A patient must permanently discontinue study treatment for any of the following:

- The patient becomes pregnant. Report the pregnancy according to instructions in Section 9.5.4
- The patient withdraws consent
- The patient experiences an AE that necessitates permanent discontinuation of Study Drug
- The patient develops laboratory test abnormalities that meet any of the stopping rules listed in Sections 8.6.1 to 8.6.3
- The patient experiences an AE that necessitates unblinding of the Investigator

The reason for discontinuation of Study Drug must be recorded in the electronic Case Report Form (eCRF) and source documentation.

Patients who early terminate from treatment will complete the Post-Treatment study procedures per the Appendix A.

For patients withdrawn for reasons other than withdrawal of consent every effort should be made to complete the early termination of study procedures and observations at the time of withdrawal (see Appendix A) and ideally within 2 weeks from the last dose of Study Drug.

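### Protocol 8.5 and 8.8 make a confirmed renal stopping criterion permanent, while 8.6 and 8.6.2 treat it as a hold with possible restart

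*Combined protocol and SAP*

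**What the plan says.** Two sections prescribe a permanent stop.

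- Protocol 8.5, Re-dosing Guidance: "If any of the stopping criteria described below (refer to Sections 8.6.1 to 8.6.6) are met, the patient will be permanently discontinued".
- Protocol 8.8 lists the events after which a patient must stop treatment for good. One is: "The patient develops laboratory test abnormalities that meet any of the stopping rules listed in Sections 8.6.1 to 8.6.3".

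Two sections describe the renal rules differently.

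- Protocol 8.6, in defining baseline, calls them "Temporary stopping rules for renal function tests".
- Protocol 8.6.2 gives two criteria, a confirmed 30% decline in eGFR and a confirmed UPCR of at least 1000 mg/g, and continues: "The possible dosing re-initiation or follow-up schedule for any events meeting either of these criteria will be determined by the Investigator". That decision requires that the sponsor's medical monitor or a designee be consulted. For smaller changes it adds that "a decision to hold or permanently stop study drug may be made based on lesser changes in these parameters", so it separates a hold from a permanent stop.

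The Amendment 4 rationale for the change to 8.6.2 says: "The updated language also clarifies the guidelines for Study Drug reinstitution". The amendment's table of changes lists no matching edit to the re-dosing text in 8.5 or to 8.8.

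**The concern.** The renal rules fall inside both ranges that demand permanent discontinuation, and neither range carries an exception. An investigator with a confirmed renal event cannot restart under 8.6.2 and also comply with 8.5 and 8.8.

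Two things are at stake. Sites can manage the same event differently, and a restart agreed with the Medical Monitor is still a deviation from two sections. In the other direction, a site that reads 8.5 and 8.8 literally ends treatment for a patient whom 8.6.2 means to keep eligible. The renal rule deserves clear wording here because Amendment 4 admits patients with eGFR down to 30 mL/min/1.73 m².

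**Working it through.** The plan gives no figure on this point, so the check is a comparison of the current sections.

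**Step 1. Does the wording of 8.5 leave room?** The softer phrasing in the Re-dosing Guidance, that dosing may in general go on, applies to patients whose retest does not meet a stopping rule. The sentence on patients who do meet one has no qualifier.

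**Step 2. Which sections do the two ranges cover, and what does each section prescribe?**

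| Section | Its own instruction | In 8.5 range | In 8.8 range | Conflict |
|---|---|---|---|---|
| 8.6.1 Liver | Permanent stop | Yes | Yes | None |
| 8.6.2 Renal | Labelled temporary; re-initiation possible | Yes | Yes | With both |
| 8.6.3 Platelets below 50,000/mm³ | Permanent stop | Yes | Yes | None |
| 8.6.3 Platelets 50,000 to below 75,000/mm³ | Pause | Not a stopping criterion | Not a stopping criterion | None |
| 8.6.4 Bleeding | Definitions only | Yes | No | None |
| 8.6.5 Potassium | Permanent stop at confirmed 6.0 mmol/L or more | Yes | No | None, but 8.8 omits it |
| 8.6.6 item 1, low BP | Permanent stop if it persists after hydration | Yes | No | None |
| 8.6.6 item 2, high BP | Permanent stop unless transient | Yes | No | Minor, with 8.5 only |

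**Step 3. Could 8.6.2 concern only unconfirmed results?** No. Both criteria require confirmation, and the re-initiation sentence refers to events that meet either of them. Those are the events that 8.5 and 8.8 make permanent.

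**Step 4. Which reading was intended?** The label in 8.6, the re-initiation sentence in 8.6.2 and the Amendment 4 rationale all point to a hold with possible restart. The rationale serves here only as evidence of intent; the conflict lies between sections now in force.

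**Step 5. Blood pressure, as a side note.** Section 8.6.6 item 2 says: "Study Drug is to be permanently discontinued unless the hypertensive event is transient and dependent on reversible initiating factors". Section 8.5 names 8.6.6 without acknowledging this exception. Item 2 also says, just before the exception, that a patient with a confirmed high reading comes off randomized treatment. Its own sentences therefore need reconciling.

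**The case against.** The best defence is that the specific rule governs the general one. Section 8.5 describes its content as guidelines, the renal section is the specific text, and all evidence of intent points the same way. The shared consultation with the Medical Monitor should also keep sites aligned in practice. Much of this stands, and it is why the point is minor. It does not remove the conflict: no clause gives 8.6.2 precedence, and 8.8 is mandatory. It is also fair to say that 8.6.2 implies a hold through its heading, the label in 8.6 and the reference to re-initiation. It does not, however, state that action.

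A reader might infer four stronger things, which the documents do not support.

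- *Platelets are another contradiction.* Section 8.6.3 does say that "dosing with Study Drug should be suspended temporarily until the platelet count has recovered to" more than 100,000/mm³. But 8.5.2, 8.6.3 and Table 5 keep that pause band apart from the permanent rule below 50,000/mm³.
- *Blood pressure is as serious as the renal conflict.* The transient-event exception is part of the rule itself, and Table 7 sets pause and stop side by side. The permanent criterion can thus be read as unmet when the event is transient, and 8.8 does not cover 8.6.6.
- *Patients may be re-exposed without supervision.* Dosing waits for the retest under 8.5, and 8.6.2 requires consultation. The literal reading of 8.5 and 8.8 errs toward stopping.
- *The primary analysis is compromised.* The PPS needs at least 10 of 12 doses. The dose due on Day d is number (d − 1)/7 + 1, so a permanent stop after a Day 57 finding leaves at most (57 − 1)/7 + 1 = 9 doses. A hold keeps the patient in only if at most two doses are missed (12 − 2 = 10). For a Day 71 finding a permanent stop leaves 11 doses, or 10 if that day's dose is withheld, so both readings satisfy the dose rule. This shows a possible route for one patient, not a bias or a loss of power.

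**Conclusion.** The renal conflict is real and wrong as written: 8.5 and 8.8 require a permanent stop for events after which 8.6 and 8.6.2 allow a restart. It is an internal inconsistency of minor weight. The 8.6.6 wording is a side note, and the platelet pause is not part of the point.

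The number of patients affected is unknown and may be zero. The Synopsis reports that no renal stopping rule was met in the two earlier Phase 2 trials, which enrolled 25 + 26 = 51 patients in all. That is reassuring but does not settle the number here. The conclusion rests on the text alone and needs no assumption about event rates. The choice of which sections to change assumes that the sponsor intends a temporary renal rule.

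**What to change.** If the renal rule is meant to be temporary:

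1. **Section 8.5.** After the statement that the patient permanently stops Study Drug, add: *except where Section 8.6.2 or the transient-event provision of Section 8.6.6 allows a hold and possible re-initiation*.
2. **Section 8.8.** Make the laboratory bullet refer to the permanent laboratory rules in 8.6.1, 8.6.3 (below 50,000/mm³) and 8.6.5. The summary of changes should say openly that this removes 8.6.2 and adds the potassium rule, which 8.6.5 already makes permanent.
3. **Section 8.6.2.** State that Study Drug is held once either criterion is confirmed, and may be re-initiated only after the Investigator consults the Sponsor Medical Monitor or designee.
4. **Section 8.6.6 item 2.** Make the sentence that takes the patient off randomized treatment subject to the transient-event exception.

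If a permanent renal stop is intended, delete the temporary label from 8.6 and the re-initiation wording from 8.6.2, and keep 8.6.2 within 8.5 and 8.8. The blood pressure edits would still be useful.

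The cost is a few wording changes, with no added visits, procedures or patients. Section 12.1 requires that the regulatory authority and IRB be informed of every amendment, and that they approve those likely to affect patient safety or trial conduct. Whether aligning the text with stated intent reaches that threshold is a judgement for the sponsor. The edits can go into the next amendment.
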